5.7.3. Laboratory assays (Amended 08 February 2019)

Please refer to [APPENDIX A](#) for a detailed description of the assays performed in the study. Please refer to [APPENDIX B](#) for the address of the clinical laboratories used for sample analysis.

The measure of immunogenicity used in this study is standard, i.e., widely used and generally recognized as reliable, accurate, and relevant (able to describe the quality and extent of the immune response). Testing will be conducted by a GSK or designated laboratory in a blinded manner towards the subject number *and* the treatment arm (*please refer to Section 5.3 Method of blinding*).

The functional measure of immunogenicity used in this study, Serum Bactericidal Assay (SBA), is a measure of the ability of antibodies, mediated with human complement, to kill meningococci, and is widely used and generally recognized as the serological correlate of protection.

The following laboratory assays are planned:

Table 7 Humoral Immunity (Antibody determination)

| System | Component | Method | Kit / Manufacturer | Unit* | Cut-off* | Laboratory |
|---------|---|--|--------------------|------------|----------|---|
| Humoral | Neisseria meningitidis serogroup A | Serum Bactericidal Assay, using human complement | In house | 1/Dilution | TBD | GSK Biologicals** or a laboratory designated by GSK Biologicals |
| | Neisseria meningitidis serogroup C | | | | | |
| | Neisseria meningitidis serogroup W | | | | | |
| | Neisseria meningitidis serogroup Y | | | | | |

TBD = to be determined

* For each of the indicator strains to be used in hSBA assays, assay cut-offs and unit will be determined following validation of the selected MenACWY hSBA format. This will be documented in the clinical report.

** GSK Biologicals laboratory refers to the Clinical Laboratory Sciences (CLS) in Rixensart, Belgium; Wavre, Belgium; or Marburg, Germany.

Additional exploratory testing on the vaccine and/or on the disease under study may be performed within the framework of the study if deemed necessary for accurate interpretation of the data or should such assay(s) become available at GSK. These assays may not be represented in the objectives/endpoints of the study protocol.

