5.7.5. Immunological correlates of protection

Although an hSBA titer ≥ 4 is an accepted correlate of protection against invasive meningococcal disease caused by *N. meningitidis* serogroup C, GSK Biologicals has historically used a more stringent immunological correlate (hSBA titer ≥ 8) for the definition of seroprotection against *N. meningitidis*.

Seropositivity cut-off or other hSBA titer values used to support ≥ 4 -fold rise definitions may change following the generation of additional qualification/validation data as expected by Center for Biologicals Evaluation and Research (CBER) to support the intended use of the MenACWY hSBAs. The values of LLOQ and LOD for each serogroup will be defined at the time of the generation of qualification and/or validation data.

The clinical endpoints used in this study are standard measures used routinely to estimate protection against meningococcal disease and have been previously agreed with CBER in the frame of *Menveo* licensure. The anticipated margin of the GMT ratio (lower limit of 0.5 for the 95% CI of the GMT ratios between groups) for study success has previously been used in the demonstration of lot-to-lot consistency in pivotal *Menveo* trials in adolescents.

The investigator is encouraged to share the immunological assay results for non-responders with the study subjects/subjects' parent(s)/LAR(s) at the end of the study, as soon as the results are available.

For the subjects identified as non-responders, it remains the responsibility of the investigator in charge of the subject's clinical management to determine the medical need for re-vaccination and to re-vaccinate the subjects as per local/regional practices. Subjects who do not achieve a ≥ 4 -fold rise in hSBA titers (according to the definition in the objectives) against any of the 4 serogroups at 1 month post-vaccination with the investigational MenACWY liquid vaccine will be offered one dose of a licensed quadrivalent MenACWY vaccine (preferably *Menveo*) after the end of the study and outside study procedures.

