10.5. Derived and transformed data

- Immunogenicity
 - Assay cut-off and unit will be determined following validation of the MenACWY hSBAs. This will be documented in the clinical report.
 - A seronegative subject is a subject whose titer is below the LOD.
 - A seropositive subject is a subject whose titer is greater than or equal to the LOD.
 - The Geometric Mean Titers (GMTs) calculations are performed by taking the anti-log of the mean of the log concentration/titer transformations. Values to be used for the antibody concentrations/titers below the assay cut-off will be described in the Statistical Analysis Plan (SAP).
 - Handling of missing data: for a given subject and a given immunogenicity measurement, missing or non-evaluable measurements will not be replaced.
- Reactogenicity and Safety
 - Handling of missing data: Subjects will be analysed to the extent that they are exposed to study vaccines and according to the available safety data for the subject during any study period. Subjects who withdraw early or who are lost to follow-up will be removed from the denominator for the time period in which they have no available safety data collected.

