APPENDIX A LABORATORY ASSAYS

The following tests will be performed using the aliquots of serum:

- The induction of functional anti-meningococcal activity by bactericidal antibodies directed against *N. meningitidis* serogroups A, C, W and Y will be determined by a Serum Bactericidal Assay using human complement (hSBA) as exogenous complement source.
- The testing will be performed at the GSK Biologicals' laboratories or a laboratory designated by GSK Biologicals. Upon validation of the hSBA format, assay cut-offs and unit for each of the MenACWY serogroups will be determined and will be documented in the clinical report. Titres will be expressed as the reciprocal of the dilution resulting in 50% inhibition.

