5.1.5. Per Protocol (PP) Set for Immunogenicity Set

PPS (Day 29) is described as all subjects in the FAS (Day 29) who:

- correctly receive the vaccine (i.e., receive the vaccine to which the subject is randomized and at the scheduled time point).
- have no protocol deviations leading to exclusion as defined prior to unblinding.
- are not excluded due to other reasons defined prior to unblinding.

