11.2. Standard data derivation

Immunogenicity

- A seronegative subject is a subject whose titer is below the LOD.
- A seropositive subject is a subject whose titer is greater than or equal to the LOD.
- Values below the limit of detection will be set to half that limit.
- Four-fold rise is defined as:
 - For individuals whose pre-vaccination titers are < LOD, the post-vaccination titers must \geq max (4*LOD, LLOQ).
 - For individuals whose pre-vaccination titers are \geq LOD and \leq LLOQ, the post-vaccination titers \geq 4*LLOQ.
 - For individuals whose pre-vaccination titers are > LLOQ, post-vaccination ≥ 4*pre-vaccination titer.
- Handling of missing data: for a given subject and a given immunogenicity measurement, missing or non-evaluable measurements will not be replaced.

Reactogenicity and Safety

• Handling of missing data: Subjects will be analyzed to the extent that they are exposed to study vaccines and according to the available safety data for the subject during any study period. Subjects who withdraw early or who are lost to follow-up will be removed from the denominator for the time period in which they have no available safety data collected.

Duration in the Study

Duration in the study is defined in days as:

Last visit date $(visit x)^a$ – Enrollment date (visit 1) + 1

^aor premature discontinuation date (in case of withdrawal from the study)

The duration is missing if one of the dates is missing or incomplete.

Unsolicited Adverse Events

All adverse events will be characterized according to the date of occurrence related to the vaccination phase as follows:

- **Emergence before vaccination phase**: start date before the first date of injection of study vaccine.
- Emergence during vaccination phase: start date on or after the first date of injection of study vaccine or, adverse event increase in severity including to "serious" adverse event.

If start date is equal to the first date of injection then "timing" variable ("On injection day, before injection"/"On injection day, after injection") will be used to define whether the adverse event occurred before or after the injection.

If an adverse event start date is missing or unknown, the adverse event will be considered as emergent.

When start and/or end dates of an adverse event are only partially known, adverse events will be categorized as emergent before, during, or after vaccination phase using the following rules:

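### Is the primary serogroup A GMT ratio left open because the plan gives no value for the limit of detection?

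*SAP*

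**What the plan says.** Protocol section 10.5 leaves the value used below the assay cut-off to the SAP. SAP section 11.2 supplies the rule: "Values below the limit of detection will be set to half that limit". It also defines serostatus: "A seropositive subject is a subject whose titer is greater than or equal to the LOD". No LOD value appears in either document.

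Protocol section 5.7.3 lists the cut-off in Table 7 as still to be determined. Its footnote says "assay cut-offs and unit will be determined following validation of the selected MenACWY hSBA format. This will be documented in the clinical report", and Appendix A says much the same: "assay cut-offs and unit for each of the MenACWY serogroups will be determined and will be documented in the clinical report". Two sentences in Protocol section 5.7.5 bear on timing. One says that the seropositivity cut-off, and other titre values behind the four-fold-rise definitions, "may change following the generation of additional qualification/validation data as expected by Center for Biologicals Evaluation and Research". The next names the LOD directly: "The values of LLOQ and LOD for each serogroup will be defined at the time of the generation of qualification and/or validation data".

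For comparison, SAP section 5.1.5 does tie something to unblinding. Subjects in the Per Protocol Set must "have no protocol deviations leading to exclusion as defined prior to unblinding". The assay limits carry no such condition. The nearest wording is in the note to the titre ≥ 8 endpoint (SAP section 4.2), which calls the LLOQ pre-defined and does not mention the LOD.

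**The concern.** A rule expressed in an unstated number is not a complete rule. On the same sera, two LOD values give two GMT ratios and two lower confidence limits, and SAP section 7.1 decides the trial on that lower limit. If the LOD is first seen in the clinical report, a reader of the plan alone cannot show that it was settled before the results were known. The LOD also enters the Day 1 titre used as the ANCOVA covariate, the four-fold-rise definition and the baseline-seronegative subgroup. The direction adds to the worry: when the liquid group has more titres below the LOD, a higher LOD pulls the ratio towards 1, which favours non-inferiority.

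**Working it through.** **1. The plan's own figure.** Inputs from Protocol section 10.3: 437 evaluable per group, SD 0.929 (log10), true ratio 0.8, margin 0.5, one-sided 0.025.
- Distance to the margin: log10(0.8) − log10(0.5) = 0.2041.
- Standard error: 0.929 × √(2/437) = 0.0628.
- Power from the noncentral t with 872 df: 0.900, matching the stated 90%.
- Enrolment: 437/0.9 = 486 per group, 972 in total.

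The LOD does not enter this calculation, so the sample size stands whatever its value.

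**2. Observed ratio needed to pass.** 0.5 × 10^(1.963 × 0.0628) = 0.664.

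**3. Effect of doubling the LOD when no titre lies between the two values.** Each substituted value rises by log10(2) = 0.301. The log10 ratio therefore moves by (pL − pC) × 0.301, where pL and pC are the shares below the LOD in the liquid and control groups. The GMT ratio is multiplied by 2^(pL − pC).
- Equal shares: no change.
- Liquid group 2, 5 or 10 percentage points higher: × 1.014, × 1.035 or × 1.072.

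**4. Log-normal illustration.** Assumptions not in the documents: log-normal titres, the shares below the LOD, and a two-fold change in LOD. The comparison is unadjusted. For mean μ, SD σ and log10 LOD L, the mean after substitution is (L − 0.301)Φ(a) + μ(1 − Φ(a)) + σφ(a), with a = (L − μ)/σ.

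Worked case: σ = 0.929, control μ = 0, 10% of control titres below the LOD, so L = −1.1906.
- Control mean: −1.4916 × 0.10 + 0.929 × 0.1755 = 0.0139.
- Liquid group at ratio 0.8: μ = −0.0969, a = −1.177, Φ = 0.1195, φ = 0.1995. Mean: −1.4916 × 0.1195 − 0.0969 × 0.8805 + 0.929 × 0.1995 = −0.0782.
- Ratio: 10^(−0.0921) = 0.809. Repeating with L + 0.301 gives 0.818.

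The pass/fail columns come from 20,000 simulated trials per setting, with both LODs applied to the same data (Monte Carlo error at most about 0.2 points).

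| Control titres below the lower LOD | Expected ratio, true 0.8 | Pass/fail differs | Expected ratio, true 0.65 | Pass/fail differs |
|---|---|---|---|---|
| 1% | 0.800 → 0.801 | 0.7% | 0.651 → 0.652 | 1.5% |
| 2% | 0.801 → 0.803 | 0.9% | 0.652 → 0.655 | 2.7% |
| 5% | 0.804 → 0.808 | 1.7% | 0.656 → 0.664 | 5.4% |
| 10% | 0.809 → 0.818 | 2.4% | 0.666 → 0.681 | 10.2% |

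With SD 0.7 the disagreement is at most 0.4% at a true ratio of 0.8, and 2.2% to 11.5% at 0.65.

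**5. Could the LOD be chosen with the results in view?** Read in order, the documents leave little room for it.
- Source: Protocol section 5.7.5 takes the LOD from assay qualification or validation, not from the treatment comparison.
- Laboratory: Protocol section 5.3 blinds it to treatment and subject number, and prevents it from linking a subject's visits.
- Sponsor: the protocol glossary entry on blinding has personnel unblinded once the data are acceptably clean, apart from serious adverse events.
- Number of looks: SAP sections 8.1, 8.2 and 9 (Amendment 1) drop the interim and analyse eCRF and laboratory data together. No planned unblinded result precedes the final one.
- Accountability: Protocol section 10.10 and SAP section 8 require departures from the statistical plan to be described and justified in the study report.

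The statement that cut-offs will be documented in the clinical report says where the value is reported. It does not say that the value is first chosen there.

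**The case for a change.** The strongest case for a change is that none of these safeguards is an explicit lock. Laboratory blinding does not bind the statisticians who apply the substitution. Seropositivity is defined by the LOD, so the sentence allowing the seropositivity cut-off to change reaches the LOD indirectly. The sponsor reopened the SAP in July 2019, noted the late serology, and still cited no value or validation report. The direction also matters. At a true ratio of 0.5 with 10% of control titres below the lower LOD (SD 0.929), the simulated pass rate is 5.1% with the lower LOD and 9.4% with the doubled one, against a nominal 2.5%.

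Most of the textual part stands: there is no value, no citation and no timing sentence. Two things limit it. The sentence about change names the seropositivity cut-off and the four-fold-rise values, which serve descriptive analyses, while the sentence that names the LOD ties it to validation. The 5.1% also arises with one fixed LOD, so most of the excess at that point belongs to substituting for low titres at all, which a timing sentence would not alter. At a 1% share the same rates are about 2.6% and 2.8%. The documents do not say which share applies.

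**Conclusion.** No change to the plan is needed. The gap is one of documentation, and analysts would fill it in the only sensible way: take the validated serogroup A LOD and halve it. Naming the value or citing the validation report would leave the LOD/2 rule, the ANCOVA, the margin of 0.5, the 437 evaluable per group and the 90% power as they are.

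At the planned ratio of 0.8 and SD 0.929, a two-fold difference in LOD changes the conclusion in 0.7% to 2.4% of simulated trials. It becomes noticeable, at 5% to 10%, only if the true ratio is about 0.65 and 5% to 10% of control titres lie below the lower LOD. These figures rest on log-normal titres, an unadjusted comparison without the Day 1 covariate, and shares and a two-fold change that the documents do not give. The judgement also assumes that validation precedes unblinding. The two documents point that way, but the validation report itself is not available here to confirm it.

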6.7.1. Recording of concomitant medications/products and concomitant vaccinations

The following concomitant medication(s)/product(s)/vaccine(s) must be recorded in the eCRF.

- All concomitant medications/products, except vitamins and dietary supplements, administered during the period of 28 days following the dose of study vaccine (Day 1 to Day 29).
- Any concomitant vaccination administered in the period starting 14 days before the dose of study vaccine and ending at Day 29.
- Prophylactic medication (i.e. medication administered in the absence of ANY symptom and in anticipation of a reaction to the vaccination).

E.g. an anti-pyretic is considered to be prophylactic when it is given in the absence of fever and any other symptom, to prevent fever from occurring (fever is defined as body temperature $\geq 38.0^{\circ}\text{C}/100.4^{\circ}\text{F}$ regardless the location of measurement). The preferred location for measuring temperature in this study will be the oral cavity.

- Any concomitant medications/products/vaccines listed in Section 6.7.2.
- During the follow-up period, after Day 29 until the last safety phone call, any concomitant medications/products/vaccines relevant to a SAE, an AE/SAE leading to withdrawal or to an AE requiring a medically attended visit to be reported as per protocol. In addition, concomitant medications relevant to SAEs need to be recorded on the expedited Adverse Event report.

6.7.2. Concomitant medications/products/vaccines that may lead to the elimination of a subject from per-protocol analyses

The use of the following concomitant medications/products/vaccines will not require withdrawal of the subject from the study but may determine a subject's evaluability in the per-protocol analysis. See Section 10.4 for analyses sets to be analysed.

- Any investigational or non-registered product (drug or vaccine) other than the study vaccines used during the study period.
- Immunosuppressants or other immune-modifying drugs defined as follows:
 - Systemic administration of corticosteroids (PO/IV/IM) within 90 days prior to informed consent, and until the Day 29 blood draw.
 - Administration of antineoplastic and immunomodulating agents or radiotherapy within 90 days prior to informed consent, and until the Day 29 blood draw.

- Long-acting immune-modifying drugs administered at any time during the study period (e.g. infliximab).

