6.5.2.6. Concomitant Medication

Medications will be coded using the GlaxoSmithKline Drug Dictionary (GSKDRUG dictionary).

The frequencies and percentages of subjects starting/reporting concomitant medication within 29 days post-vaccination will be summarized overall and by study group.

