- If the partial end date is before (<) the study vaccination (i.e., year or year & month is/are before the study vaccination year or year & month) then the adverse event is emergent before vaccination phase.
- If the partial start date is equal or after (≥) the study vaccination (i.e., year or year & month is/are after or the same as the study injection year or year & month) then the adverse event is emergent during vaccination phase.

205343 (MENACWY CONJ-032 [V59_71]) Statistical Analysis Plan Amendment 1 Final

The maximum event severity is the greatest severity associated with a preferred term for a reported adverse event according to the following order: Mild < Moderate < Severe. Unknown/ Missing severity is considered as severe (except for the definition of emergence).

Multiple AEs with the same PT for the same subject are counted only once.

Vaccination-related Adverse Events are those for which the cause has been evaluated by the investigator, and recorded either as related or unknown/missing.

Prestudy, Concomitant and Post-Vaccination Medications

A **previous medication** is a medication used only before the first study vaccination (i.e. medication end date < first study vaccination date).

A **post-vaccination** medication is a medication used only after the second blood draw

All other medications are **concomitant**.

When start and/or end dates of a medication intake are missing, the medication is considered as concomitant with the study vaccination schedule.

If the study vaccination date is missing then the medication is considered as concomitant with the study vaccination schedule, provided that the study vaccine was administered to the subject.

The frequencies and percentages of subjects will be summarized overall and by study group.

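### The SAP's missing-date rule for medications overrides a known date that already settles the class, in two kinds of record; only descriptive summaries are affected

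*SAP*

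**What the plan says.** SAP 11.2, under the paragraph on prestudy, concomitant and post-vaccination medications, sets three classes.

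- Previous: the test is "medication end date < first study vaccination date", which needs the end date only.
- Post-vaccination: such a "medication is a medication used only after the second blood draw", so a start date after that draw is sufficient.
- Concomitant: the residual class ("All other medications are" concomitant).

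The missing-date rule follows: "When start and/or end dates of a medication intake are missing, the medication is considered as concomitant with the study vaccination schedule". It makes no exception for a record whose remaining date already fixes the class, and no order of precedence is given.

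The only medication table the SAP names is in 6.5.2.6. It covers subjects "starting/reporting concomitant medication within 29 days post-vaccination". SAP 11.2 also ends its medication rules with a general statement that frequencies and percentages will be given by group, without saying for which classes.

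Protocol 6.7.1 determines which medications reach the database. It includes the products listed in 6.7.2, some of them used before consent, and it extends past Visit 2: "During the follow-up period, after Day 29 until the last safety phone call, any concomitant medications/products/vaccines relevant to a SAE", with the same provision for events leading to withdrawal or to a medically attended visit.

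**The concern.** A missing-date convention should fill in what is not known. Here the phrase joining start and end dates means that a single gap sends the record to the concomitant class, even when the date in hand rules that class out. Two adjoining rules then give the same record two incompatible classes, and a programmer has to choose between them.

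The adverse-event rules in the same section work the other way and use whatever part of a date is known ("If the partial end date is before (<) the study vaccination" places the event before the vaccination phase). The medication rule discards information that is at least as good.

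At stake is the meaning of the concomitant class. It can take in products that could not have been in use between vaccination and the second serum sample, at the expense of the other two classes.

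**Working it through.** The plan states no figure on this point, so there is nothing to reproduce. The check is an enumeration of the SAP's own definitions.

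**Inputs.** Vaccination is on Day 1 and the second draw on nominal Day 29 (SAP Section 2). Known dates run over Day -90 to Day 181, an assumed grid on which Day 0 is the day before vaccination. With both dates known, the definitions read: end < Day 1 gives previous; start > Day 29 gives post-vaccination; anything else is concomitant.

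**Step 1.** For each record with one date missing, list every class the definitions allow over all possible values of the missing date, and compare with the class the missing-date rule assigns.

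| Missing | Known date | Grid days | Classes the definitions allow | Class by the rule |
|---|---|---|---|---|
| start | end, Day -90 to 0 | 91 | previous only | concomitant (contradiction) |
| start | end, Day 1 to 29 | 29 | concomitant only | concomitant |
| start | end, Day 30 to 181 | 152 | concomitant or post-vaccination | concomitant (default) |
| end | start, Day -90 to 0 | 91 | previous or concomitant | concomitant (default) |
| end | start, Day 1 to 29 | 29 | concomitant only | concomitant |
| end | start, Day 30 to 181 | 152 | post-vaccination only | concomitant (contradiction) |

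The contradiction holds on 91 of 91 grid days in the first row (case a) and on 152 of 152 in the last (case b). In the other four rows the rule is either correct or a cautious choice between classes that cannot be told apart. The grid counts show that the logic has no exceptions; they say nothing about how often such records occur.

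**Step 2: can these records arise?** Case (a): the list in protocol 6.7.2 covers systemic corticosteroids in the 90 days before consent without a minimum duration, whereas exclusion criterion 7 concerns courses of more than 14 consecutive days. A subject with a short earlier course can therefore be enrolled and have it recorded, possibly with only the stop date known. Case (b): products linked to a reportable event after Day 29 are recorded up to the last call, and the end date may be missing.

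**Step 3: what reaches the named table?** Counting vaccination day as the first, as SAP 6.5.2.3 does, the window in SAP 6.5.2.6 is Days 1 to 29. Visit 2 may fall 21 to 42 days after Visit 1, that is, Days 22 to 43. A case (b) product starts after the draw, so it can start inside the window only if Visit 2 was held on Days 22 to 28. Products first reported at the Day 91 or Day 181 calls fall outside it. Most of case (b) therefore stays out of this table. Case (a) records could enter it, because a product ended before vaccination can still be reported within the window.

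**Step 4: size per subject.** Planned group size is about 486, so one subject is 1/486 = 0.0021, or about 0.2 percentage points. This is a ceiling: summaries count subjects, and someone already counted for another concomitant product adds nothing.

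**The case against.** The strongest reply is that little follows from this, and most of that reply stands.

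- **Ongoing treatments.** A reader might infer that every long-term treatment started during follow-up is misclassified. The documents do not support that. The SAP never says that ongoing status counts as a missing end date. If it is treated as information that use continues, a start after the second draw gives the post-vaccination class, correctly.
- **Output.** The 29-day window removes most of case (b) from the one table the SAP names. Separate tables of previous and post-vaccination medication are not specified, so an understatement of those classes in a report is plausible but not established.
- **Frequency.** Case (a) is narrow. General medication is recorded only from Day 1 to Day 29. Earlier use is limited to vaccines from 14 days before the dose, prophylactic medication and the 6.7.2 list, much of which overlaps the exclusion criteria.
- **Size.** A reader might assume that some share of subjects, say 1 to 5%, is affected and conclude that the concomitant class gains as many points. No such share has a source in the documents, and counting by subject makes the conversion an upper bound in any case.
- **Decisions.** Per-protocol exclusion uses codes 1040 and 2040 (SAP 5.2.2.1 and Annex 2), which are not tied to these classes. SAP 6.5.2 plans no statistical comparison of safety parameters between groups.

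None of this removes the contradiction. A table window does not correct a derived class, and caution is a reason to default when the class is unknown, not when it is known.

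**Conclusion.** The point holds as a drafting error of limited reach. For the two kinds of record in the first and last rows of the table, the missing-date rule gives a class that the SAP's own definitions exclude, and no other provision settles which prevails. It would be wrong to infer that the medication classes as a whole are unsound: the default does its job wherever the known date is not decisive.

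The size is at most about 0.2 percentage points of a group summary per affected subject, on the planned 486 per group. The number of such subjects cannot be derived from the documents. How much case (b) matters depends on how ongoing medication is coded. The serogroup A GMT ratio, the non-inferiority decision and membership of the per-protocol set do not depend on these classes. The change is worth making because it is cheap, not because a conclusion is at risk.

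**What to change.** Replace the missing-date sentence in SAP 11.2 with wording such as:

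> If a start or end date is missing, the medication is considered concomitant unless the available date shows that it ended before vaccination (previous) or started after the second blood draw (post-vaccination). An ongoing medication is classified by its start date: post-vaccination if it started after the second blood draw, otherwise concomitant.

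The last clause prevents an ongoing product that started before vaccination from being read as previous. The cost is this wording change and a small adjustment to the derivation program. No new data are needed, and no other analysis changes.
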